14.5 Subject Confidentiality

Subject confidentiality is strictly held in trust by the participating investigators, their staff, and the sponsor(s) and their agents. This confidentiality is extended to cover testing of biological samples and genetic tests in addition to the clinical information relating to participating subjects.

The study protocol, documentation, data, and all other information generated will be held in strict confidence. No information concerning the study or the data will be released to any unauthorized third party without prior written approval of the sponsor.

The study monitor or other authorized representatives of the sponsor may inspect all documents and records required to be maintained by the investigator, including but not limited to, medical records (office, clinic, or hospital) and pharmacy records for the subjects in this study. The clinical study site will permit access to such records.

14.6 Study Discontinuation

If the study is discontinued, enrolled subjects will continue to be followed for safety assessments.

Subjects will be compensated for their participation in this study. Compensation will be in accordance with the local IRB's policies and procedures and subject to IRB approval.

14.7 Future Use of Stored Specimens

No specimens will be saved for future use. Once the study has been completed DMID will instruct the site and Fisher BioServices to destroy all residual samples. The destruction of residual samples will be appropriately documented.

15 DATA HANDLING AND RECORD KEEPING

The investigator is responsible to ensure the accuracy, completeness, legibility, and timeliness of the data reported. All source documents should be completed in a neat, legible manner to ensure accurate interpretation of data. Black ink is required to ensure clarity of reproduced copies. When making changes or corrections, cross out the original entry with a single line, and initial and date the change. **DO NOT ERASE, OVERWRITE, OR USE CORRECTION FLUID OR TAPE ON THE ORIGINAL.**

Copies of the electronic CRF (eCRF) will be provided for use as source documents and maintained for recording data for each subject enrolled in the study. Data reported in the eCRF derived from source documents should be consistent with the source documents or the discrepancies should be explained

DMID and/or its designee will provide guidance to investigators on making corrections to the source documents and eCRF.

15.1 Data Management Responsibilities

All source documents and laboratory reports must be reviewed by the clinical team and data entry staff, who will ensure that they are accurate and complete. Adverse events must be graded, assessed for severity and causality, and reviewed by the site PI or designee.

Data collection is the responsibility of the clinical trial staff at the site under the supervision of the site PI. During the study, the investigator must maintain complete and accurate documentation for the study.

The EMMES Corporation will serve as the Statistical and Data Coordinating Center for this study and will be responsible for data management, quality review, analysis, and reporting of the study data.

15.2 Data Capture Methods

Clinical data (including AEs, concomitant medications, and reactogenicity data) and clinical laboratory data will be entered into a 21 CFR Part 11-compliant Internet Data Entry System (IDES) provided by The EMMES Corporation. The data system includes password protection and internal quality checks, such as automatic range checks, to identify data that appear inconsistent, incomplete, or inaccurate. Clinical data will be entered directly from the source documents.

15.3 Types of Data

Data for this study will include safety, laboratory studies, EKG data and pharmacokinetic data for the study drug.

15.4 Timing/Reports

Safety data will be reviewed by the SMC per the SMC charter for this study. The SMC will review available safety data for Groups 1-3, after the third study group has completed the day 10 study visit. A second report will be generated approximately 6-8 months after study completion that will include all unblinded safety data for groups 1-4. Interim statistical reports may be generated as deemed necessary and appropriate by DMID.

15.5 Study Records Retention

Study documents should be retained for a minimum of 2 years after the last approval of a marketing application in an ICH region and until there are no pending or contemplated marketing applications in an ICH region or at least 2 years have elapsed since the formal discontinuation of clinical development of the investigational product. These documents should be retained for a longer period, however, if required by local regulations. No records will be destroyed without the written consent of the sponsor, if applicable. It is the responsibility of the sponsor to inform the investigator when these documents no longer need to be retained.

15.6 Protocol Deviations

A protocol deviation is any noncompliance with the clinical trial protocol, Good Clinical Practice (GCP), or Manual of Procedures requirements. The noncompliance may be either on the part of the subject, the investigator, or the study site staff. As a result of deviations, corrective actions are to be developed by the site and implemented promptly.

These practices are consistent with ICH E6:

4.5 Compliance with Protocol, sections 4.5.1, 4.5.2, and 4.5.3

5.1 Quality Assurance and Quality Control, section 5.1.1

5.20 Noncompliance, sections 5.20.1, and 5.20.2.

It is the responsibility of the site to use continuous vigilance to identify and report deviations within 5 working days of identification of the protocol deviation, or within 5 working days of the scheduled protocol-required activity. All deviations must be promptly reported to DMID, via The EMMES Corporation's IDES or via the TRI/ICON DMID-Clinical Research Operations and

Management Support (CROMS) email ([contact]), web-
(www.dmidcroms.com) or fax-based system ([name]).

Note: Those sites participating in trials with a designated 'central unit' will follow the reporting requirements specified in their protocols and MOPs. The 'central unit' will be responsible for submission of the protocol deviation information to TRI/ICON DMID-CROMS.

All deviations from the protocol must be addressed in study subject source documents. A completed copy of the DMID Protocol Deviation Form (TRI/ICON DMID-CROMS or IDES form) must be maintained in the regulatory file, as well as in the subject's source document. Protocol deviations must be sent to the local IRB/IEC per their guidelines. The site PI/study staff is responsible for knowing and adhering to their IRB/IEC requirements.

16 PUBLICATION POLICY

Following completion of the study, the investigator is expected to publish the results of this research in a scientific journal. The International Committee of Medical Journal Editors (ICMJE) member journals have adopted a trials-registration policy as a condition for publication. This policy requires that all clinical trials be registered in a public trials registry such as ClinicalTrials.gov^{*}, which is sponsored by the National Library of Medicine. Other biomedical journals are considering adopting similar policies. It is the responsibility of DMID to register this trial in an acceptable registry. Any clinical trial starting enrollment after 01 July 2005 must be registered on or before patient enrollment. For trials that began enrollment prior to this date, the ICMJE member journals will require registration by 13 September 2005, before considering the results of the trial for publication.

The ICMJE defines a clinical trial as any research project that prospectively assigns human subjects to intervention or comparison groups to study the cause-and-effect relationship between a medical intervention and a health outcome. Studies designed for other purposes, such as to study pharmacokinetics or major toxicity (e.g., Phase I trials), would be exempt from this policy.

APPENDIX A: SCHEDULE OF EVENTS**Groups 1,2 and 3**

		Follow Up Visits										
		Screening Study Visit 00	Baseline Study visit 01	Study Visit 02	Study Visit 03	Study Visit 04	Study Visit 05	Study Visit 06	Study Visit 07	Study Completion Visit 08	Unscheduled Visit	Early Termination Visit
Study Day		D-28 to -1	D1	D2	D3	D4	D5	D6	D8	D10		
Visit Window		N/A	N/A	N/A	N/A	N/A	N/A	N/A	+/-1	+/-2		
Signed Consent Form		X										
Assessment of Eligibility Criteria		X	X	X	X	X	X					
Enrollment			X									
Review of Medical History		X	X								X	X
Review of Concomitant Medications		X	X	X	X	X	X	X	X	X	X	X
Administration of Study Medication			X	X	X	X						
Physical Examination	Complete	X	X									
	Symptom- Directed			(X)	(X)	(X)						
	Vital Signs	X	X	X	X	X	X	X	X	X	(X)	X
Assessment of Adverse Events and SAEs		X	X	X	X	X	X	X	X	X	X	
Clinical Laboratory	Chemistry	X	X		X		X		X	X		X
	Hematology	X	X		X		X		X	X		X
	Coagulation Studies	X	X		X		X		X	X		X
	Serology	X										
	Urinalysis	X	X		X		X		X	X		X
	Pregnancy Test	X	X									
Research Laboratory	PK studies 10 mL whole blood		X	X	X	X	X	X	X	X		X

Groups 1,2 and 3		Follow Up Visits										
		Screening Study Visit 00	Baseline Study visit 01	Study Visit 02	Study Visit 03	Study Visit 04	Study Visit 05	Study Visit 06	Study Visit 07	Study Completion Visit 08	Unscheduled Visit	Early Termination Visit
Study Day		D-28 to -1	D1	D2	D3	D4	D5	D6	D8	D10		
Visit Window		N/A	N/A	N/A	N/A	N/A	N/A	N/A	+/-1	+/-2		
Other Procedures	EKG	X	X		X		X		X			

(X) – As indicated/appropriate.

Hematology – Hemoglobin, WBC and neutrophil count, platelet count.

Biochemistry – **Screening**: creatinine, ALT, AST, random glucose, total bilirubin.

– **Follow Up Visits**: creatinine, sodium, potassium, chloride, carbon dioxide, blood urea nitrogen ALT, AST, total bilirubin.

Coagulation Studies– INR, and partial thromboplastin time (PTT)

Serology – Hepatitis B surface antigen, hepatitis C antibody, human immunodeficiency virus (HIV)

Urinalysis – Urine Dipstick for protein and glucose

Research Laboratory – **Days 1 and 5**: 10 mL blood for baseline PK (prior to drug administration), 10 mL blood at 30 minutes, 1, 2, 3, 4, 6, 9, and 12 hours (all times have a window of +/- 15 minutes except the 9 and 12 hour samples which have a window of +/- 30 minutes)

Day 2: 10 mL blood prior to study drug administration-approximately 24 hours after dosing on previous day (+/- 4 hours) and 2 hours after study drug administration (+/- 20 minutes)

Days 3 and 4: 10 mL blood prior to study drug administration-approximately 24 hours after dosing on previous day (+/- 2 hours)

Day 6: 10 mL blood-approximately 24 hours after dosing on previous day (+6hours)

Group 4		Follow Up Visits								
		Screening Study Visit 00	Baseline Study visit 01	Study Visit 02	Study Visit 03	Study Visit 04	Study Visit 05	Study Completion Study Visit 06	Unscheduled Visit	Early Termination Visit
Study Day		D-28 to -1	D1	D2	D4	D8	D9	D14		
Visit Window		N/A	N/A	N/A	N/A	+/-1	N/A	+/-2		
Signed Consent Form		X								
Assessment of Eligibility Criteria		X	X			X				
Randomization/Enrollment			X							
Review of Medical History		X	X						X	X
Review of Concomitant Medications		X	X	X	X	X	X	X	X	X
Administration of Study Medication			X			X				
Physical Examination	Complete	X	X							
	Symptom-Directed			(X)	(X)	(X)	(X)	(X)	(X)	X
	Vital Signs	X	X	X	X	X	X	X	(X)	X
Assessment of Adverse Events and SAEs			X	X	X	X	X	X	X	X
Clinical Laboratory	Chemistry	X	X		X			X		X
	Hematology	X	X		X			X		X
	Coagulation Studies	X	X		X			X		X
	Serology	X								
	Urinalysis	X	X		X			X	(X)	X
	Pregnancy Test	X	X			X				
Research Laboratory	PK Studies 10 mL whole blood		X	X		X	X	X		X
Other Procedures	EKG	X	X			X				

(X) – As indicated/appropriate

Hematology – Hemoglobin, WBC and neutrophil count, platelet count.

Biochemistry – **Screening**: creatinine, ALT, AST, random glucose, total bilirubin.

– **Follow Up Visits**: creatinine, sodium, potassium, chloride, carbon dioxide, blood urea nitrogen ALT, AST, total bilirubin.

Coagulation Studies– INR and partial thromboplastin time (PTT)

Serology – Hepatitis B surface antigen, hepatitis C antibody, human immunodeficiency virus (HIV)

Urinalysis – Urine Dipstick for protein and glucose

Research Laboratory – **Days 1 and 8**: 10 mL blood for baseline PK (prior to drug administration), 10 mL blood at 30 minutes, 1, 2, 3, 4, 6, 9, and 12 hours (all times have a window of +/- 15 minutes except the 9 and 12 hour samples which have a window of +/- 30 minutes)

Day 2 and 9: 10 mL blood –approximately 24 hours following study drug dose (+/- 4 hours)

APPENDIX B: DMID ADULT TOXICITY TABLES NON-SERIOUS ADVERSE EVENTS

ABBREVIATIONS: Abbreviations utilized in the Tables:

ULN = Upper Limit of Normal IV = Intravenous

LLN = Lower Limit of Normal

Clinical Adverse Events			
VITAL SIGNS	Grade 1	Grade 2	Grade 3
Fever (°C) **	38.0 – 38.4	38.5 – 38.9	≥39.0
Fever (°F) **	100.4 – 101.1	101.2 – 102.0	>102.0
** Oral temperature; no recent hot or cold beverages or smoking. A protocol should select either °C or °F for inclusion.			
Tachycardia – beats per minute	101 – 115	116 – 130	> 130 or ventricular dysrhythmias
Bradycardia – beats per minute	50 – 54 or 45-50 bpm if baseline 5-60 bpm. For athletically trained individuals with a pulse 45-49, grade 1 abnormality = pulse 40-44	45 – 49 or 40-44 bpm if baseline 50-60 bpm. For athletically trained individuals with a pulse 45-49, grade 2 abnormality = pulse 35-39	< 45 or <40 bpm if baseline 50-60 bpm. For athletically trained individuals with a pulse 45-49, grade 3 abnormality = pulse less than 35 or pulse 35-45 with symptoms of lightheadedness, exercise intolerance, syncope
Hypertension (systolic)- mm Hg**	141-150	151-160	> 160
Assuming supine position, 10 min at rest conditions, not sleeping subjects, measurements on the same arm and several concordant results.			
Hypertension (diastolic) – mm Hg**	91-95	96-100	> 100
Hypotension (systolic) – mm Hg**	85-89	80-84	< 80
Tachypnea – breaths per minute	23-25	26-30	>30
CARDIOVASCULAR	Grade 1	Grade 2	Grade 3

Arrhythmia		Asymptomatic, transient signs, no Rx required	Recurrent/persistent; symptomatic Rx required
Hemorrhage, Blood Loss	Estimated blood loss \leq 100 mL	Estimated blood loss > 100 mL, no transfusion required	Transfusion required
RESPIRATORY	Grade 1	Grade 2	Grade 3
Cough	Transient- no treatment	Persistent cough;	Interferes with daily activities
Bronchospasm, Acute	Transient; no treatment; 71% - 80% FEV1 of peak flow	Requires treatment; normalizes with bronchodilator; FEV1 60% - 70% (of peak flow)	No normalization with bronchodilator; FEV1 <60% of peak flow
Dyspnea	Does not interfere with usual and social activities	Interferes with usual and social activities, no treatment	Prevents daily and usual social activity or requires treatment
GASTROINTESTINAL	Grade 1	Grade 2	Grade 3
Nausea	No interference with activity	Some interference with activity	Prevents daily activities
Vomiting	No interference with activity or 1 – 2 episodes/24 hours	Some interference with activity or > 2 episodes/24 hours	Prevents daily activity or requires IV hydration
Diarrhea	2 – 3 loose or watery stools	4 – 5 loose or watery stools	6 or more loose or watery stools or requires IV hydration
Reactogenicity			
SYSTEMIC	Grade 1	Grade 2	Grade 3
Allergic Reaction	Pruritus without rash	Localized urticaria	Generalized urticaria; angioedema or anaphylaxis

Headache	No interference with activity	Repeated use of non-narcotic pain reliever > 24 hours or some interference with activity	Significant; any use of narcotic pain reliever or prevents daily activity
Fatigue	No interference with activity	Some interference with activity	Significant; prevents daily activity
Myalgia	No interference with activity	Some interference with activity	Significant; prevents daily activity
All Other Conditions	Grade 1	Grade 2	Grade 3
Illness or clinical adverse event (as defined according to applicable regulations)	No interference with activity	Some interference with activity not requiring medical intervention	Prevents daily activity and requires medical intervention

Laboratory Adverse Events			
Blood, Serum, or Plasma *	Grade 1	Grade 2	Grade 3
Sodium – Hyponatremia mEq/L	132 – <LLN	130 – 131	<130
Sodium – Hypernatremia mEq/L	>ULN – 148	149 – 150	>150
Potassium – Hyperkalemia mEq/L	>ULN – 5.2	5.3 – 5.4	>5.4
Potassium – Hypokalemia mEq/L	<LLN-3.1	<3.1 – 3.0	<3.0
CO ₂	1-2 mEq/L above or below normal	3-4 mEq/L above or below normal	5 or more mEq/L above or below normal
Chloride	1-3 mEq/L above or below normal	4-5 mEq/L above or below normal	6 or greater above or below normal
Glucose – Hypoglycemia mg/dL	65 – 67	55 – 64	<55
Glucose – Hyperglycemia Fasting (water is permitted) – mg/dL	>ULN – 120	121 – 130	>130
Glucose – Hyperglycemia Random – mg/dL	140 – 159	160 – 200	>200
Blood Urea Nitrogen mg/dL	23-26	27 – 31	> 31
Creatinine – mg/dL	>ULN – 1.7	1.8 – 2.0	>2.0
Calcium – hypocalcemia mg/dL	8.0 – <LLN	7.5 – 7.9	<7.5
Calcium – hypercalcemia mg/dL	>ULN – 11.0	11.1 – 11.5	>11.5
Magnesium – hypomagnesemia mg/dL	1.3 – 1.5	1.1 – 1.2	<1.1
Phosphorous – hypophosphatemia mg/dL	2.3 – 2.5	2.0 – 2.2	<2.0
CPK – mg/dL	400-1000	1001-1500	>1500
Albumin – Hypoalbuminemia g/dL	2.8 – 3.0	2.5 – 2.7	< 2.5
Total Protein – Hypoproteinemia g/dL	5.5 – <LLN	5.0 – 5.4	< 5.0
Alkaline phosphate – U/L	132-240	241– 360	>360
AST U/L	44 – 105	106-175	>175
ALT U/L	44 – 105	106-175	>175
Bilirubin (serum total) mg/dL	1.3 – 2.0	2.1 – 2.5	> 2.5
Bilirubin – when ALT \geq 105 (Hy's law)	1.3 -1.5	1.6 – 2.0	> 2.0
Amylase- U/L	200-270	271-360	>360
Lipase- U/L	176-270	271-360	>360
Hemoglobin (Female) – g/dL	11.0 – 11.5	9.5 – 10.9	< 9.5
Hemoglobin (Male) – g/dL	12.0 – 12.5	10.0 – 11.9	<10.0
WBC Increase – cell/mm ³	11,001 – 15,000	15,001 – 20,000	> 20,000

WBC Decrease – cell/mm ³	2,500 – 3,500	1,500 – 2,499	< 1500
Lymphocytes Decrease – cell/mm ³	750 – 1,000	500 – 749	< 500
Neutrophils Decrease – cell/mm ³	1,500 – 2,000	1,000 – 1,499	< 1000
Eosinophils – cell/mm ³	500-750	751-1500	> 1500
Platelets Decreased – cell/mm ³	120,000 – 130,000	100,000 – 119,999	<100,000
INR –(International Normalized Ratio of the prothrombin time)	1.3 to <1.7	1.8- <2.3	≥ 2.4
PTT – seconds (partial thromboplastin time)	>ULN-42.1	42.2– 50.0	> 50.0
Fibrinogen increase – mg/dL	>ULN – 500	501 – 600	> 600
Fibrinogen decrease – mg/dL	<LLN – 140	125 – 139	<125
Urine *	Grade 1	Grade 2	Grade 3
Protein	1+	2+	>2+
Glucose	1+	2+	>2+
Blood (microscopic) – red blood cells per high power field (rbc/hpf)	5-10	11-50	> 50 and/or gross blood

* The laboratory values provided in the tables serve as guidelines and are dependent upon institutional normal parameters.

* Institutional normal reference ranges should be provided to demonstrate that they are appropriate.

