After all eight subjects have completed the 10 day follow up period, an electronic safety review of the electronic data will be performed and the SDCC will issue a report to DMID stating that the predefined halting rules have or have not been met. If none of the predefined safety events (any study drug related SAE, any study drug related Grade 3 AE or laboratory abnormality or two study drug related Grade 2 AEs or laboratory abnormalities in the same laboratory parameter) have occurred (one study drug related two sequential subjects (one at a time with 7 days between each subject) DMID will approve enrollment into the second dose group (7.5 mg/kg oxfendazole daily x 5 days) and will be monitored for a total of 7 days each for predefined adverse events prior to enrolling the remaining subjects in the group. After the 10 day follow up period has been completed for group 2, an electronic safety review will be completed and if no predefined events have occurred two sequential subjects (one at a time with 7 days between each subject) will be enrolled into the third dose group (15 mg/kg oxfendazole daily x 5 days) and will be monitored for a total of 7 days each for predefined safety events prior to enrolling the remaining subjects in the group.

For the multiple ascending dose evaluation, between 8 and 24 subjects will be enrolled. This number should be small enough to perform the study safely and efficiently, yet large enough for an estimation of the oxfendazole PK and the identification of any common side effects of oxfendazole following multiple doses.

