- Fasting (water is permitted) subjects will remain fasting (water is permitted) for two hours after the administration of drug.
- Fed subjects will receive a high fat breakfast. Approximately 30 minutes (+/- 15 minutes) following completion of the meal, the study nurse will administer a single 3 mg/kg oral dose of oxfendazole.
- Lunch and dinner will be provided. Subjects will be allowed to eat snacks but will be asked to avoid drinking grapefruit juice and excessive (>2 cups) coffee.
- 10 mL of blood for oxfendazole level will be drawn at 30 minutes, 1, 2, 3, 4, 6, 9, and 12 hours (all times have a window of +/- 15 minutes except the 9 and 12 hour samples which have a window of +/- 30 minutes- it is critical to record the exact time of blood draw).
- Perform EKG approximately 2 hours following study drug (+/- 20 minutes)
- Assess AEs and SAEs throughout the day and prior to discharge from the CRU.
- Counsel on need to avoid alcohol, drugs, tobacco and medications throughout the study.
- Counseling on avoidance of pregnancy.

7.6 Follow-up – GROUP 4

Clinic Visit 02, Day 2

- Vital signs including oral temperature, blood pressure, and pulse will be obtained.
- A targeted physical exam may be performed, if indicated.
- Review concomitant medications
- Review for AEs and SAEs
- Draw 10 mL of blood for oxfendazole level -approximately 24 hours after dosing on day 1 (+/- 4 hours)
- Counsel on need to avoid alcohol, drugs, tobacco and medications throughout the study.

Clinic Visit 03, Day 4

- Vital signs including oral temperature, blood pressure, and pulse will be obtained.
- A targeted physical exam may be performed, if indicated.
- Review concomitant medications
- Review for AEs and SAEs
- Collect 15 mL of blood for safety panels (hemoglobin, white blood cell count, including neutrophil and eosinophil counts, platelet count, INR, partial thromboplastin time, Na, K, Cl, CO₂, blood urea nitrogen, creatinine, ALT, AST, and total bilirubin).
- Collect urine for dipstick testing for protein and glucose.
- Remind subjects to remain fasting (water is permitted) for 8 or more hours prior to study visit 04.

-
- Counsel on need to avoid alcohol, drugs, tobacco and medications throughout the study.

Clinic Visit 04, Day 8 (+/- 1 day)

- Vital signs including oral temperature, blood pressure, and pulse will be obtained.
- Review inclusion/exclusion criteria (including assessment of time of last oral food intake).

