9.2 Methods and Timing for Assessing, Recording, and Analyzing Safety Parameters

9.2.1 Adverse Events

Adverse Event:

ICH E6 defines an AE as any untoward medical occurrence in a patient or clinical investigation subject administered a pharmaceutical product regardless of its causal relationship to the study treatment. An AE can therefore be any unfavorable and unintended sign (including an abnormal laboratory finding), symptom, or disease temporally associated with the use of medicinal (investigational) product. The occurrence of an AE may come to the attention of study personnel during study visits and interviews of a study recipient presenting for medical care, or upon review by a study monitor.

All AEs including local and systemic reactions not meeting the criteria for “serious adverse events” should be captured on the appropriate CRF. Information to be collected includes event description, time of onset, clinician’s assessment of severity, relationship to study product (assessed only by those with the training and authority to make a diagnosis, which would include MD, PA, Nurse Practitioner, DO, or DDS), and time of resolution/stabilization of the event. All AEs occurring while on study must be documented appropriately regardless of relationship. All AEs will be followed to adequate resolution.

Any medical condition that is present at the time that the patient is screened should be considered as baseline and not reported as an AE. However, if it deteriorates at any time during the study, it should be recorded as an AE.

All AEs must be graded for severity and relationship to study product.

FDA defines an AE as any untoward medical occurrence associated with the use of a drug in humans, whether or not considered drug related.

Severity of Event: All AEs will be assessed by the clinician using a protocol defined grading system. For events not included in the protocol defined grading system, than the following guidelines will be used to quantify intensity.

Grade 1: Mild: events require minimal or no treatment and do not interfere with the patient's daily activities.

Grade 2: Moderate: events result in a low level of inconvenience or concern with the therapeutic measures. Moderate events may cause some interference with functioning.

Grade 3: Severe: events interrupt a patient's usual daily activity and may require systemic drug therapy or other treatment. Severe events are usually incapacitating.

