9.5 Halting Rules

9.5.1 Sentinel Subject Halting Rules

For each of the multiple dose ascending groups (Groups 1-3), one sentinel subject will be dosed and monitored for 7 days after receiving the first dose of study product. If there are no

predefined safety events, a second sentinel subject will be enrolled and followed for a total of 7 days. If none of the sentinel subjects' halting criteria are met:

- any study drug related SAE
- any study drug related grade 3 AE or laboratory abnormality
- any two Grade 2 AE or laboratory abnormalities of the same laboratory parameter that are study drug related

then the remaining subjects in each group may be enrolled.

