9.5.2 Dose Escalation Halting Criteria

Prior to dose escalation to the next cohort, the Statistical and Data Coordinating Center (SDCC) will notify the study PIs, DMID medical monitor (MM), and DMID Independent Safety Monitor (ISM) whether the below dose escalation criterion were met. Following enrollment and 10 days of safety follow up of the eight subjects in the dose group.

Dose escalation will not proceed if any of the following dose escalation criteria occur:

- any study drug related SAE
- any study drug related grade 3 AE or laboratory abnormality
- any two Grade 2 AE or laboratory abnormalities of the same laboratory parameter

In addition to these criteria, dose escalation may also stop for other reasons per the advice of the SMC, ISM, or DMID Medical Monitor for further evaluation, discussion, and recommendations from the SMC.

If the above dose escalation halting criteria are NOT met, the dose escalation may proceed with agreement of DMID.

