APPENDIX D: UNIVERSITY OF IOWA NORMAL LABORATORY VALUES

	Male	Female
Complete Blood Count		
WBC	3.7-10.5 k/mm ³	3.7-10.5 k/mm ³
Hemoglobin	13.2-17.7 g/dl	11.9-15.5 g/dl
Platelets	150-400 k/mm ³	150-400 k/mm ³
Hemogram plus Automated Differential		
Neutrophils	2188-7800/mm ³	Same
BUN	10-20 mg/dl	Same
Creatinine	0.6-1.2 mg/dl	0.5-1.0 mg/dl
Alanine Aminotransferase (ALT)	0-41 u/l	0-33 u/l
Aspartate Aminotransaminase (AST)	0-40 u/l	0-32 u/l
Chloride	95-107	Same
CO ₂	22-29 mEq/L	Same
Potassium	3.5-5.0	Same
Sodium	135-145	Same
Total Bilirubin	<=1.2 mg/dL	Same
Prothrombin Time	9-12 seconds	Same
Partial Thromboplastin Time	22-31 seconds	Same
INR	0.9-1.2	Same
Glucose (random)	<140	Same
Urinalysis, Routine Screen (using Reflectance Spectrophotometry)	Specific gravity: 1.000-1.029; pH: 5.0-9.0, Dipstick negative for protein, hemoglobin, bilirubin, urobilinogen, ketones, glucose, leukocyte esterase and nitrite	Same
Urine Microscopy	0-5 WBC, 0-2 RBC	Same
Pregnancy Test		Positive = pregnant Negative = not pregnant
Hepatitis B Surface Antigen	Negative	Same
HIV Types 1&2 Antibody	Non-Reactive	Same
Hepatitis C Virus Antibody, Version 2.0	Negative	Same

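### The INR row of Protocol Appendix B leaves 1.7 and 2.3 without a grade, so two drug-related INRs of 2.3 fall outside a two-Grade-2 rule that two of 2.2 would meet

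*Protocol*

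**What the plan says.** The INR row of Protocol Appendix B (Laboratory Adverse Events) prints the three grades as "1.3 to <1.7 1.8- <2.3 ≥ 2.4". Appendix D gives the site reference range to one decimal: "INR 0.9-1.2 Same".

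Grades feed two predefined criteria:

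- **Sentinel step, section 9.5.1.** The rest of a group may not be enrolled after "any two Grade 2 AE or laboratory abnormalities of the same laboratory parameter that are study drug related".
- **Dose escalation, section 9.5.2.** Escalation does not proceed after "any two Grade 2 AE or laboratory abnormalities of the same laboratory parameter". This bullet does not mention relatedness, but section 4 (Study Design) states the same escalation criterion as study drug related.

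Section 4 adds that, after an electronic review, "the SDCC will issue a report to DMID stating that the predefined halting rules have or have not been met".

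Three other provisions bear on a value with no grade:

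- Section 9.2.1 has a general mild/moderate/severe scale: "For events not included in the protocol defined grading system, than the following guidelines will be used to quantify intensity".
- A footnote to Appendix B says: "The laboratory values provided in the tables serve as guidelines and are dependent upon institutional normal parameters".
- Section 9.2.3 says that results outside the local reference range but not considered Grade 1 abnormalities are not adverse events and are not graded.

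**The concern.** A severity scale that feeds a stopping criterion should not skip a value that is worse than one it counts. As printed, 2.2 is Grade 2, 2.3 has no grade and 2.4 is Grade 3, so the two-Grade-2 criterion is not monotone in INR.

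Two further uses of the grades are touched. Section 11.4.3 promises graded laboratory summaries by cohort and study day, and results of 1.7 and 2.3 have no printed grade to enter. Under section 9.2.3 read literally, such results would not be recorded as adverse events either. That sentence was probably written for values milder than Grade 1, but it offers no route to a grade for 2.3.

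Coagulation is part of the planned safety monitoring, and section 2.3.1 names the liver as a principal target organ in animals at higher doses. The row is therefore in active use.

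**Working it through.** **1. Apply the printed bands.** The inputs are the INR row of Appendix B and one-decimal reporting. The latter is an assumption, taken from the form of the Appendix D range.

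| INR | Printed grade | Grade with contiguous bands |
|---|---|---|
| 0.9-1.2 | normal | normal |
| 1.3-1.6 (4 values) | 1 | 1 |
| 1.7 | none | 1 |
| 1.8-2.2 (5 values) | 2 | 2 |
| 2.3 | none | 2 |
| 2.4 and above | 3 | 3 |

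From 1.3 to 2.3 there are 4 + 1 + 5 + 1 = 11 one-decimal values, of which 2 have no grade. At two decimals the gaps are 1.70-1.79 and 2.30-2.39, so finer reporting does not close them.

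**2. Check whether the row is an isolated slip.** Appendix B has 23 rows for laboratory parameters measured after dosing:

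- hemoglobin (female, male), WBC (increase, decrease), neutrophils, eosinophils, platelets: 7
- INR, PTT: 2
- sodium (low, high), potassium (low, high), CO₂, chloride, BUN, creatinine: 8
- AST, ALT, bilirubin, bilirubin with ALT ≥105: 4
- urine protein, urine glucose: 2

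The sum is 7 + 2 + 8 + 4 + 2 = 23. Eosinophils are included because the Group 4 Day 4 panel in section 7.6 lists them ("including neutrophil and eosinophil counts, platelet count, INR"). In 22 rows each grade runs on to the next at the printed precision; in PTT, for example, Grade 1 ends at 42.1 and Grade 2 starts at 42.2. INR is the only exception.

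**3. Apply the two-Grade-2 criterion.** Take two study-drug-related results, so that the comparison holds whether or not 9.5.2 requires relatedness.

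- 2.2 and 2.2: two Grade 2 results, criterion met.
- 2.3 and 2.3: no Grade 2 result under the printed table, criterion not met.
- A single related result of 2.4 is Grade 3 and meets the Grade 3 criterion by itself.

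The gap at 1.7 does not reach these criteria if 1.7 is taken as Grade 1. It bears on adverse-event status and on the graded summary.

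**4. Count the results exposed.** Assume full enrollment, no missing or repeat samples and no replaced subjects. Day 1 laboratories are drawn before dosing and are not counted.

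- Groups 1 and 2, days 3, 5, 8 and 10: 2 groups × 8 subjects × 4 days = 64. All precede an escalation decision.
- Group 3 is the top dose and has no next cohort, so only its two sentinels count, within their 7-day watch (days 3, 5 and 8): 2 × 3 = 6.
- Results bearing on 9.5.1 or 9.5.2: at most 64 + 6 = **70**.
- Results graded in the whole trial: Groups 1-3, 3 × 8 × 4 = 96; Group 4, days 4 and 14, 12 × 2 = 24; total **120**.

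The documents give no basis for the probability of an INR of exactly 2.3, so none is calculated.

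**The case against.** The strongest reply is that this is a symbol slip with no practical consequence. Reading each strict limit as less than or equal closes both gaps at one decimal. Sections 9.2.1 and 15.1 put grading with clinicians and the site investigator, and the table values are guidelines. A clinician facing 2.3, between a Grade 2 and a Grade 3 value, would naturally call it Grade 2. Screening INR must be normal (section 5.1), and section 9.5.2 lets the SMC, ISM or Medical Monitor stop escalation for other reasons.

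Most of this stands, and it keeps the severity low. It does not supply a grade. The general scale in 9.2.1 is for events outside the grading system, and INR is inside it. That scale also rests on daily activity and treatment, so an asymptomatic 2.3 would not reliably come out as moderate. The footnote assigns no grade to 2.3. Discretion to stop is a backstop, not a predefined criterion. Reading the limits as less than or equal still leaves 1.71-1.79 and 2.31-2.39 open if INR is reported to two decimals.

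Three stronger readings are tempting, and the documents do not support them:

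- A reader might infer that the data system would let a 2.3 pass unnoticed. Section 9.6.2 says only that a computerized system acquires halting data, and no document shows how 2.3 is coded.
- A reader might infer that all 96 results in Groups 1-3 come under 9.5.1 and 9.5.2. Section 9.5.1 covers sentinels only, and Group 3 has no next cohort.
- A reader might infer from the 9.5.2 bullet alone that escalation stops on unrelated Grade 2 results. Section 4 states that criterion as drug related.

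**Conclusion.** The gap is real and no other text closes it: INR 1.7 and 2.3 have no printed grade, in 1 of 23 relevant rows. Of the two, 2.3 bears on the sentinel and escalation criteria, and at most 70 INR results come under those criteria. Both values bear on adverse-event reporting and on the graded summary, which covers 120 results.

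The conclusion that 2.3 fails to count holds for the table as printed. It does not say that a stop would be missed in practice; that would need INRs at this value in volunteers screened to a normal INR, no clinician grade and no discretionary stop. The counts rest on the enrollment and sampling assumptions stated above. The severity is a minor correction, worth making because the row feeds predefined stopping criteria.

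**What to change.** Make the INR bands contiguous and keep the printed floors of all three grades: Grade 1, 1.3 to <1.8; Grade 2, 1.8 to <2.4; Grade 3, ≥2.4. No value that now has a grade changes grade, 1.7 becomes Grade 1 and 2.3 becomes Grade 2, and nothing from 1.3 upward is left ungraded at any precision. The documents do not state these cut-points, so the sponsor should confirm them, and any grading check in the data system should be matched to them.

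The cost is an edit to one row of Appendix B and to any corresponding data check. There is no added burden on subjects.
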